46    relationship to emotional well-being and functional communication, treatment that  
47    improves naming deficits will positively influence quality of life in many of these individuals.  
48    The approach taken to remediate naming deficits in aphasia is to treat impaired WM systems

1 on the premise that certain cognitive processes underlie linguistic functions in aphasia. This  
2 approach represents a departure from most behavioral-based naming treatment approaches,  
3 but reflects a growing recognition that WM systems in individuals with aphasia impact  
4 linguistic performance . The addition of a-tDCS as a neuromodulation tool to increase  
5 cortical excitability (upregulate) the working memory center to target naming is a novel  
6 approach in aphasia. These findings, , will provide valuable information regarding the role  
7 WM plays in naming and the potential benefit of using neuromodulation to the DLPFC to  
8 influence naming in aphasia.

9

- 10 • **Is the design of the study appropriate for the questions that are posed?**

11

12 *Treatment Design:*

13 A single subject cross-over design with a 4 week wash out period will be used. Two treatment  
14 conditions will be presented. The sham (SHAM) condition will consist of presentation of sham  
15 tDCS for 20 minutes followed by behavioral naming treatment. The real treatment condition  
16 (REAL) will consist of 20 minutes of a-tDCS to the left DLPFC followed by behavioral naming  
17 treatment. The length of behavioral naming treatment will depend on how long each participant  
18 takes to go through the treatment stimuli twice. A SHAM-REAL sequence will be used across all  
19 participants. Although order effects may be introduced using the same sequence across  
20 participants, the small number of participants makes it difficult to interpret any data that comes  
21 from using a counterbalanced presentation of treatment.

22 Treatment will be provided over five consecutive days. A minimum of a one-month washout  
23 period will be provided between the two conditions (Figure 1). Prior to initiating the REAL  
24 treatment condition, the naming RTs obtained on the second word list during the pre-treatment  
25 testing period (prior to the initiation of the SHAM condition) will be compared to the naming RTs  
26 obtained after the washout period. RTs will be analyzed to ensure that no lasting treatment  

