27 effects remain after the SHAM condition. If performance on naming RTs is +/- 1 standard  
28 deviation from the individual's benchmark mean, the REAL treatment condition will begin. If  
29 performance on naming RTs is > +/- 1 standard deviation from the individual's benchmark  
30 mean, REAL treatment will be postponed until the mean RTs fall within +/- 1 standard deviation  
31 of the benchmark. Periodic checks will be conducted weekly to identify when to begin REAL  
32 condition. Once there are minimal differences between naming RTs on the second word list,  
33 the REAL treatment will be initiated.

34

[figure not shown]
35 *Outcome measures:*

36 Two different word lists will be generated; a different list will be used for each treatment  
37 condition to control for exposure and learning effect. Pretreatment testing outcome measures will  
38 be recorded for 5 consecutive days for each outcome measure including: 1) naming accuracy 2)  
39 naming RTs on both word lists 3) performance on motor speech tasks and 4) performance on  
40 working memory tasks. Stability of baseline performance, defined as no more than 20%  
41 difference between scores, will be obtained in five consecutive sessions. In addition, outcome  
42 measures will be obtained immediately after each treatment session. Five maintenance  
43 outcome measures will also be obtained upon completion of treatment. These sessions will take  
44 place at the Clinical Translational Science Institute (CTSI) on [name] on the University  
45 of MN campus. An adverse events questionnaire will also be given after each treatment session  
46 as a mechanism of participants reporting any discomfort.

47  
48  
49

50

1 **Figure 1. Treatment Schedule**

6 *tDCS Protocol.*

7 Treatment sessions will take place at the University of MN Clinical Translational Science  
8 Institute. Each participant will be seated comfortably in a chair. A swim cap will be placed on  
9 the participant's head to identify cranial landmarks for accurate electrode placement. The area  
10 referred to as F3 by the International 10/20 system for electroencephalogram electrode  
11 placement has been established as the optimal location for targeting the left DLPFC.  
12 The F3 region will be located by marking the vertex (the midpoint between left and right tragus  
13 and midpoint between nasion and inion), measuring the head circumference. When these  

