14 measurements are entered into the Beam F3 Locator Software, additional values are provided  
15 to reliably identify the location of F3. Once F3 has been established, two saline soaked surface  
16 sponge electrodes (35cm) will be prepared and placed. For optimal anodal stimulation to the  
17 DLPFC, the anode will be placed over F3 and the cathode will be placed over the right  
18 supraorbital region. A current of 2mA will be delivered for 20 minutes  by a multichannel  
19 transcranial current stimulator (Starstim, Neuroelectrics Corporation; Cambridge, MA). a-tDCS  
20 will be applied before and during behavioral treatment in the design specified below.

25 *Behavioral-Based Naming Treatment Protocol.*

27 *Stimuli.* Eighty black-and-white line drawings will be obtained from on-line clip art websites.  
28 Picture names will be normed using five to ten English-speaking volunteers who will be asked to  
29 provide the names of the pictures. Cues words will be paired with the pictures if the words  
30 represent an associative or thematic relationship. Therefore, the words will be chosen that  
31 represent a concrete attribute (e.g., the picture, SHARK, is paired with the cue word *teeth*),  
32 location (e.g., the picture, SHARK, is paired with the cue word *ocean*), and either function or  
33 category (e.g., the picture, SHARK, is paired with the cue word, *fish*). The selection criteria for  
34 choosing these particular attributes is based on a classification criteria of thematic relations .  
35 Moreover, there is empirical evidence that that associative relations would prove beneficial in a  
36 naming treatment paradigm . Commonly used phrases (e.g., *great white shark*) or compound  
37 words (e.g., *bluefin shark*), synonyms or antonyms will be excluded. These cue words will be  
38 obtained from a semantic features normative database , which provides not only semantic

1 features information but categorical information as well. Two lists of 20-items will be created,  
2 which will be presented to each participant in order to avoid presenting the same list across the  
3 conditions. Pictures used in both lists will be balanced in terms of visual complexity and  
4 familiarity ratings. Words used in all conditions will be balanced in terms of lexical frequency  

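### The plan reads as pairing one word list with SHAM and the other with REAL throughout, so a list that is easier to train could pass for a stimulation effect in all four participants

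*Combined protocol and SAP*

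**What the plan says.** The relevant text is spread over three parts of the combined protocol and SAP.

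- **Treatment Design.** "A SHAM-REAL sequence will be used across all" participants. The reason given for not counterbalancing is that four participants are too few to interpret a counterbalanced order of treatment. Before REAL starts, "treatment condition, the naming RTs obtained on the second word list during the pre-treatment" period are compared with those after washout. REAL begins "Once there are minimal differences between naming RTs on the second word list".
- **Outcome measures.** "Two different word lists will be generated; a different list will be used for each treatment" "condition to control for exposure and learning effect". Pretreatment measures run over five days, and RTs are explicitly taken on both lists.
- **Stimuli.** "Two lists of 20-items will be created", "which will be presented to each participant in order to avoid presenting the same list across the" conditions. Pictures are balanced on visual complexity and familiarity, and words on lexical frequency and length. The frequency look-up is described for the cue words, so it is not clear that the target names are balanced on frequency.

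The Aim 2 analysis compares conditions within each subject, using means with 95% confidence intervals, a standardised effect size for naming accuracy, and visual inspection. It has no list term. No section says how a list is allocated to a condition.

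**The concern.** Separate lists stop practice on one set of pictures from carrying into the other condition. They also create a second difference between conditions, namely the pictures themselves. If list 2 is always the REAL list, each within-participant REAL-SHAM comparison of treated items is also a list 2 versus list 1 comparison.

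Hypothesis 2 predicts improvement after REAL but not after SHAM. With four participants and no pooled test, much of the support for it would come from the same pattern appearing in each person. A shared list difference can produce that agreement without any effect of stimulation. If the difference favours the SHAM list, it can hide a real effect.

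The stated reason for not counterbalancing concerns the order of treatments. It does not bear on which list goes with which condition, and that can be swapped while the order stays fixed.

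**Working it through.** **Inputs from the documents.** Four participants, two treated lists of 20 items, one SHAM-REAL order, and 40 untreated control pictures. The picture count is consistent: 2 × 20 + 40 = 80, matching "Eighty black-and-white line drawings will be obtained from on-line clip art websites". The plan gives no power, alpha, item SD or participant SD, so it has no figure of its own to reproduce. All SDs and list differences below are assumptions.

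**1. Bias by pairing.** Let D be the difference between lists in gain (list 2 minus list 1), and k the number of the four participants who have list 2 under REAL. The bias in the mean REAL-SHAM contrast is D × (2k − 4)/4.
- Fixed pairing, k = 4: bias = D × 4/4 = D.
- 2:2 swap, k = 2: bias = D × 0/4 = 0.

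**2. How large D could be.** If items differ in gain with residual SD s after balancing, the SD of D is s × √(2/20) = 0.316 × s.

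| Assumed s (points) | SD of D (points) | 95% range of D (points) |
|---|---|---|
| 10 | 3.2 | ±6 |
| 20 | 6.3 | ±12 |
| 30 | 9.5 | ±19 |

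A D of 5 or 10 points is therefore plausible over part of this range, but not established.

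**3. Chance that all four favour REAL with no true effect.** Let σ be the participant-level SD of the REAL-SHAM difference, and p = Φ(D/σ), with D favouring the REAL list under fixed pairing. Fixed pairing gives p⁴. A 2:2 swap gives p²(1 − p)². With no list difference the value is 0.5⁴ = 0.0625.

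| D (points) | σ (points) | p | Fixed | 2:2 swap |
|---|---|---|---|---|
| 5 | 5 | 0.841 | 0.501 | 0.018 |
| 5 | 10 | 0.691 | 0.229 | 0.046 |
| 5 | 15 | 0.631 | 0.158 | 0.054 |
| 10 | 5 | 0.977 | 0.912 | <0.001 |
| 10 | 10 | 0.841 | 0.501 | 0.018 |
| 10 | 15 | 0.748 | 0.312 | 0.036 |

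If D is 5 points against the REAL list and σ is 10, fixed pairing gives (1 − 0.691)⁴ = 0.009, so the error can run either way.

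**4. Unrestricted randomisation.** An independent coin flip per participant gives all four the same pairing with probability 2 × 0.5⁴ = 0.125, and a 2:2 split with probability 6/16 = 0.375. The 2:2 split has to be imposed.

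**The case against.** **The pairing is inferred.** A reader might conclude that the same physical list is tied to the same condition in every participant. The documents do not state this. The second word list could mean the list a given participant receives second, and the schedule figure is not available. What can be said is that no allocation rule is given and that the text most naturally reads as fixed.

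**Raw difficulty overstates the threat.** A reader might size the problem by how much two 20-item lists differ in raw accuracy. With item difficulty SDs of 0.5, 1.0 and 1.5 logits at about 50% accuracy, that gap has an SD of 3.7, 6.6 and 8.6 points. But the plan takes baselines and analyses accuracy as an effect size. If every item gains an equal 1.5 logits, the list gap in gain has an SD of only 1.4, 2.5 and 3.1 points. Unequal trainability would add to this, by an amount the documents cannot supply.

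**Speed is largely visible.** A stable RT difference between lists should appear in the five-day baseline, and comparing each list with its own baseline would remove it. This stands, except that the Aim 2 text does not say the cross-condition RT comparison is baseline-corrected.

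**The error need not be identical in all four.** Items that are hard for one person and easy for another would not repeat. Only the shared part of a list difference recurs.

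**A swap does less than it may seem to.** A reader might infer that it shows whether an advantage follows stimulation or list. REAL always comes second, so an advantage that follows REAL could still be order. Within one participant list and condition stay confounded, and two against two is a weak basis for separating a list effect from differences between people.

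**Feasibility and safety are the stated primary purpose.** This lowers the stakes. Even so, naming accuracy and RT are listed among the primary outcomes, and Aim 2 addresses effectiveness.

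**Conclusion.** The concern holds in a limited form. The plan gives no rule for allocating lists to conditions and, followed as it most naturally reads, confounds list with condition for treated-item naming accuracy and RT. The balancing variables and the baseline reduce the risk but do not control how well a list responds to training. The untreated control list cannot show this either, because it is not trained.

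The size is unknown. With an assumed σ of 10 points and no true effect, an assumed list difference in gain of 5 or 10 points towards the REAL list raises the chance of a four-out-of-four pattern favouring REAL from 0.0625 to 0.23 or 0.50. A 2:2 swap brings it to 0.046 or 0.018. These figures assume that the list difference is common to all participants and that participant-level differences are normal and independent. They illustrate the mechanism and do not estimate it for this trial. The case for the change is that it costs almost nothing. It does not rest on evidence that the lists differ.

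**What to change.** 1. State the pairing rule. Keep the SHAM-REAL order and, before baseline, assign lists at random with a forced 2:2 split: list A with SHAM and list B with REAL for two participants, and the reverse for the other two.
2. Compare each list with its own baseline in the cross-condition analysis of accuracy and RT.
3. Label plots by list as well as condition, so that a list effect can be seen as opposite patterns between the two pairs.
4. In the washout check, replace the reference to the second word list with *the list assigned to REAL*.
5. State as limitations that the swap leaves the order effect in place and that list and condition remain confounded within each participant.

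The cost is a few sentences and slightly more bookkeeping. No extra items, visits or participants are needed.

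### Separate word lists avoid re-treating the same items but do not equalise test exposure: list 1 enters SHAM after 5 tests, list 2 enters REAL after at least 6

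*Combined protocol and SAP*

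**What the plan says.** Treatment Design fixes one order for everyone: "takes to go through the treatment stimuli twice. A SHAM-REAL sequence will be used across all" participants. Each condition has five daily sessions, and the two are separated by at least a month: "Treatment will be provided over five consecutive days. A minimum of a one-month washout" period.

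Outcome measures gives each condition its own list. The reason for doing so, and the start of the testing plan, read "condition to control for exposure and learning effect. Pretreatment testing outcome measures will" and continue "be recorded for 5 consecutive days for each outcome measure including: 1) naming accuracy 2", then "naming RTs on both word lists 3) performance on motor speech tasks and 4) performance on" working memory tasks. So both lists are named on five days before anything is treated. The same section repeats the outcome measures after every treatment session and at five maintenance tests, without naming the lists used there.

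List 2 has a further role. Before REAL starts, Treatment Design takes "treatment condition, the naming RTs obtained on the second word list during the pre-treatment" period and specifies that those from the "testing period (prior to the initiation of the SHAM condition) will be compared to the naming RTs" obtained after washout. If the mean reaction time (RT) lies more than 1 SD from the participant's benchmark, REAL waits and the check is repeated: "of the benchmark. Periodic checks will be conducted weekly to identify when to begin REAL". No upper limit on the number of re-checks is given.

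The Stimuli text adds 40 untreated control pictures, restricted to baseline and post-treatment testing. The Aim 2 analysis paragraph scores naming accuracy as an effect size against benchmarks of 4.0, 7.0 and 10.1, and compares RTs through means, 95% confidence intervals and visual inspection. It does not say which baseline the REAL result is measured from.

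**The concern.** Naming the same pictures repeatedly can speed responses and raise accuracy without any treatment. A two-list design keeps items treated under SHAM from being treated again under REAL. It does not by itself ensure that the two lists have been tested equally often when their own treatment begins. Here the list used for the washout check is the list about to be treated under REAL, so each check is also a practice trial on REAL outcome items. List 1 has no counterpart to this.

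The check can also feed itself. If practice speeds list-2 RT beyond 1 SD of benchmark, REAL is postponed and list 2 is named again a week later.

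Hypothesis 2 predicts improvement after real stimulation but not after sham. With four participants, one sequence and comparison by eye, no step in the analysis would separate a difference in test practice from a difference in stimulation.

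**Working it through.** The plan states no exposure count, so there is no figure to reproduce. The counts below are built from the schedule.

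**Inputs**
- Pre-SHAM tests of each list: 5 (Outcome measures; timing for list 2 from Treatment Design).
- Treatment sessions per condition: 5, each followed by one outcome test (lists not named).
- Maintenance tests: 5 (lists not named; not stated whether they follow each condition).
- Post-washout check of list 2: 1, plus *w* weekly re-checks with no limit stated.

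**Tests before a list's own treatment**
- List 1 before SHAM: 5.
- List 2 before REAL: 5 + *a* + *b* + 1 + *w*. Here *a* is the number of list-2 tests after SHAM sessions (0 or 5), and *b* is the number at SHAM maintenance (0 or 5).

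| Reading of the SHAM-block tests | List 2, *w* = 0 | Excess over list 1 | List 2, *w* = 4 |
|---|---|---|---|
| List 2 not probed (*a* = *b* = 0) | 5 + 1 = 6 | 1 | 10 |
| Probed after each session (*a* = 5) | 5 + 5 + 1 = 11 | 6 | 15 |
| Also at SHAM maintenance (*a* = *b* = 5) | 5 + 5 + 5 + 1 = 16 | 11 | 20 |

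The first row follows from the text as written. The other two depend on which lists are probed, which the text leaves open. Figure 1, the treatment schedule, is not shown in the copy read here and may settle it.

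**What the excess could be worth.** This is an illustration on assumed inputs, none of which is in the documents. Suppose accuracy is scored against the pre-SHAM baseline, each extra test adds *g* = 0.1 to 0.5 items, and the baseline SD is 1 to 2 items. The practice contribution to the effect size is *g* × excess / SD:
- Excess 1: from 0.1 × 1 / 2 = 0.05 to 0.5 × 1 / 1 = 0.5.
- Excess 6: from 0.1 × 6 / 2 = 0.3 to 0.5 × 6 / 1 = 3.0.
- Excess 11: from 0.1 × 11 / 2 = 0.55 to 0.5 × 11 / 1 = 5.5.

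The plan's small benchmark is 4.0. One extra test stays far below it. Among the extremes shown, only the largest assumed gain with the smallest SD and 11 extra tests exceeds it. The formula allows neither a plateau nor forgetting over the washout, so the upper values lean high.

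**If REAL is instead scored from a baseline re-measured just before it**, practice already gained sits in the starting level and is not counted as change. On a 20-item list, a higher start may leave less room to improve, which works against REAL.

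**What the 1 SD rule does.** It holds the RT shift carried into REAL to at most 1 SD of benchmark. It places no condition on accuracy.

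**The case against.** The strongest reply is that the plan never claims equal test counts. It says that each treatment condition has its own list, and the Stimuli text explains this as a way to avoid showing the same list in both conditions. On that natural reading the two lists do their job. This stands: a reader might infer that the plan's statement about exposure is false, but the documents support only the narrower point that separate lists leave test exposure unequal.

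Second, a reader might infer that list 2 is named 16 or more times before REAL. The phrase about both word lists occurs only in the pre-treatment sentence, and the maintenance tests are described as following the completion of treatment, not each condition. The certain excess is one test, plus any weekly re-checks. One test is little beside five sessions that each go through the items twice.

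Third, a reader might infer that practice is credited to real stimulation. That requires scoring REAL from the pre-SHAM baseline. It is the only baseline described, but the analysis text does not say that it is the one used, and a later baseline could turn the bias the other way. The direction of the exposure imbalance is fixed; the direction of any bias is not.

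Fourth, the 1 SD rule limits the RT shift, and the untreated pictures give a partial check on practice. Both points stand in part. Accuracy is not covered by the rule, and the control pictures are not scheduled to receive the extra checks given to list 2.

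Finally, the plan concedes possible order effects and cites its small size as the reason not to counterbalance. That concession does not dispose of the point, because test exposure can be equalised within the same fixed order.

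**Conclusion.** The point holds in limited form. List 2 enters REAL after at least 6 tests against 5 for list 1, plus one per weekly re-check without a stated limit. The imbalance runs the same way in every participant because the order is fixed. The counts of 11 and 16 are conditional on list 2 being probed during the SHAM block.

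The effect on the result is also conditional: possible inflation of the REAL effect with the pre-SHAM baseline, possible loss of room for gain with a later one. The documents give no figure for practice gain per test, so the size of the bias cannot be stated; the effect-size range above only illustrates it. At the certain minimum it is likely to be small. This is a worthwhile, inexpensive improvement and a needed clarification. It does not show that a difference favouring REAL would be due to practice.

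**What to change.** 1. In the SHAM block, use list 1 and not list 2 for naming probes, and say in Outcome measures which lists are named at each visit.
2. Run the post-washout and weekly RT checks on a reserved subset of the 40 control pictures, chosen in advance and named at baseline. List 2 receives no treatment in SHAM, and neither do these pictures, so they can serve the same purpose of detecting a lasting general effect. Amend the Stimuli text, which now limits control pictures to baseline and post-treatment testing, and leave the subset out of the generalisation comparison.
3. Keep one list-2 probe just before REAL as a fresh baseline check, and give list 1 one matching probe just before SHAM. Each list then enters its own treatment after 5 + 1 = 6 tests.
4. State which baseline the REAL effect uses, and report the number of prior tests per list and participant.

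The cost is wording in Treatment Design, Outcome measures, Stimuli and the Aim 2 analysis, one extra list-1 probe, fewer control pictures for generalisation, and fewer looks at list 2 before REAL. Spacing would still differ, since list 2's five baseline tests would be at least a month old when REAL begins. The single late probe shows whether its level has moved in the meantime.
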